##### **Cohort 1 Suspected neutropenic sepsis:**

60 patients will be approached over a three-month period to participate in Cohort 1. If 80% of those approached are recruited (are eligible and provide consent), 48 patients will provide a 95% confidence interval of 68.2% to 88.2%. The widest the 95% confidence interval would be, with an estimated proportion of 50%, 37.7% to 62.3%.

If a valid OLO neutrophil test result is obtained from 90% of recruited patients, 43 patients will provide a 95% confidence interval of 77.8% to 95.5%. If a survey is completed and returned by 80% of recruited patients, 38 patients will provide a 95% confidence interval of 65.7% to 88.3%. In both instances, the widest the 95% confidence interval would be, with an estimated proportion of 50%, 36.4% to 63.6%.

##### **Cohort 2 Borderline neutropenia/pre SACT evaluation:**

30 patients will be approached over a three-month period to participate in Cohort 2. If 80% of those approached are recruited (are eligible and provide consent), 24 patients will provide a 95% confidence interval of 62.7% to 90.5%. The widest the 95% confidence interval would be, with an estimated proportion of 50%, 33.2% to 66.9%.

If a valid investigational device test result is obtained from 90% of recruited patients, 22 patients will provide a 95% confidence interval of 74.2% to 97.7%.

##### **Cohort 3 Survey Only**

24 patients will be approached over a one-three month period to participate in WP1 Cohort 3. If 80% of those approached are recruited (are eligible and return an anonymous survey), 19 patients will provide a 95% confidence interval of 59.5% to 90.8%.

In all instances, the widest the 95% confidence interval would be, with an estimated proportion of 50%, 31.4% to 68.6%.

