## 5.3 Secondary outcomes measure(s)

### ***Feasibility of recruiting patients and use of the OLO (Sight Diagnostics) system:***

- Proportion of those recruited from those consented and/or approached
- Proportion of recruited participants with a valid (as opposed to an invalid test result) from all recruited participants. A valid result is when the OLO system neutrophil result is  $\pm 0.2 \times 10^9/L$  of the laboratory gold standard result;
- Proportion of recruited participants returning the follow-up survey from all recruited participants;
- Number and type of OLO System (Sight Diagnostics) device flags and error codes raised during device operation for fingerprick versus venous blood sample to assess device accuracy;
- Number of re-takes of finger prick versus venous blood sample to assess device accuracy.
- Number of cases in which a discrepancy between the OLO System and gold standard would change the management of the patient, according to retrospective clinical review.
- Number of patients with valid OLO System test results for:
  - Haemoglobin – (validity  $\pm 0.7$  g/L)
  - Platelets – (validity  $\pm 15 \times 10^9/L$ )
  - Lymphocytes – (validity  $\pm 0.3 \times 10^9/L$ )

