The discussion group meeting will be manually recorded in anonymised written note format and summarised in anonymised digital format (for example Microsoft Word). The summary will be used to assess the acceptability of the device and application to patients and their carers. It will also be used to develop a participant acceptability survey that, following approval by REC, will be used as a patient evaluation tool to assess acceptability of the equipment. This patient evaluation tool will be completed by participants of WP1, the device cohort comparator study, Cohorts 1-3.

This work will assist in the design of a larger trial and will involve liaison with:

- VPLG.
- Wales Cancer Research Centre (WCRC).
- Tenovus.
- Healthcare workers.

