##### **Cohort 3: Patients who have not had blood assessed by the OLO device but have received therapy that can cause a low white blood cell count.**

- 1) 18 years old or over
- 2) Patients receiving or who have received cytotoxic chemotherapy or radiotherapy

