## **15 Analysis**

### **15.1 Quantitative analysis of WP1 device cohort evaluation**

All quantitative analysis will be documented in the SAP [36] prior to implementation of the analysis.

As this is a feasibility study, statistical analysis of study outcomes will be descriptive in nature. Continuous data will be reported as means and standard deviations, or medians and interquartile ranges, as appropriate. Categorical data will be reported as frequencies and proportions. Outcomes will be estimated with their associated 95% confidence intervals.

No formal hypothesis testing will take place.

While subsequent funding is not formally linked to satisfying any specific progression criteria, we propose the following as indicators that a larger study is feasible (NB. Failure to meet one or more of the criteria would indicate that modifications are required, with potentially further feasibility testing, prior to a larger study) as described in Table 7.

**Table 7.** Trial progression criteria

Outcome	Criteria
Recruitment	At least 80% of patients approached to take part provide consent
Intervention adherence	At least 90% of recruited participants receive the OLO test
Intervention fidelity	A valid test result is obtained from at least 90% of recruited participants who receive the OLO test
Survey fidelity	A survey is completed and returned from at least 80% of recruited participants who are given the survey
Data collection	At least 80% of recruited participants have clinical outcome data available for statistical analysis
Staff focus groups	Focus group data indicates that the OLO test is acceptable
Patient focus groups	Focus group data indicates that the OLO test is acceptable

There will be no interim analyses other than TMG review of WP1 SAE's at TMG meetings, Trial Manager review of screening logs through the WP1-3 recruitment phases, and Trial Manager review of data entry after approximately half of the participants have been recruited to WP1.

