#### **15.4 Cost effectiveness analysis**

In WP4 the TMG will analyse health utility and economic data (for example bed usage, antibiotic treatment and blood test costs) collected in WP1 via various routine UKONS data collection, a local audit of UKONS data run in parallel to the WP1 device cohort study, and WP1 patient surveys, to identify key cost drivers. The results will be used to inform the design of a future larger UK-wide trial, including anticipated effect sizes for the larger trial, which will include a cost utility study.

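### The survey return rate has no consistent denominator or population, so the same 19 returns can read as 100%, 79.2% or 20.9%

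*Protocol*

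**What the plan says.** **The rate**

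- Section 14.1.1, Cohort 3, plans on 24 patients approached: "If 80% of those approached are recruited (are eligible and return an anonymous survey), 19 patients will provide". The stated 95% interval is 59.5% to 90.8%. Section 9.1.1 agrees that returning the form is itself the implied consent.
- Section 15.1, Table 7, sets the survey progression criterion: "A survey is completed and returned from at least 80% of recruited participants who are given the survey".
- Section 5.3 lists the feasibility outcome as "Proportion of recruited participants returning the follow-up survey from all recruited participants".
- Section 6.1.3 calls the 24 patients participants at the point when they receive the survey, and section 12.1.3 uses the word in the same way. Section 9.3.1 sets 19 returns as the minimum.

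**Who is surveyed**

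- Sections 6.1.3 and 12.1.3, the Cohort 3 block of Table 2, section 12.5 and the source-data Table 8 assign the survey to Cohort 3. Section 8.1.1 heads that cohort "Patients who have not had blood assessed by the OLO device but have received therapy".
- Section 6.2 says otherwise: "This patient evaluation tool will be completed by participants of WP1, the device cohort comparator study, Cohorts 1-3". The lay summary (section 3.2) also says that patients from the device part will be asked to complete it.
- Section 14.1.1 still plans precision for a Cohort 1 survey: "If a survey is completed and returned by 80% of recruited patients, 38 patients will provide" an interval of 65.7% to 88.3%. It gives no survey figure for Cohort 2.

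**The concern.** A return rate needs one numerator, one denominator and one population. Here the word recruited carries the denominator in both Table 7 and section 5.3, but for Cohort 3 section 14.1.1 makes it the numerator. If that definition is carried into Table 7, the same people are counted above and below the line and the criterion carries no information. If the section 5.3 wording is applied across WP1, 72 device-cohort patients who, under the procedures, never receive a survey enter the denominator.

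Table 7 is meant to show whether a larger study is feasible, and section 15.1 says that missing a criterion points to modifications and perhaps further feasibility testing. A criterion whose value depends on the section followed cannot serve that purpose. Separately, the Cohort 1 survey interval describes precision for data that the procedures do not collect.

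**Working it through.** **Inputs.** Cohort 3: 24 approached, 19 returns planned (14.1.1, 9.3.1). Device cohorts: 48 + 24 = 72 recruited (9.3.1). Cohort 1 survey: 38 of 48 (14.1.1). Criterion: 80% (Table 7).

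**1. Reproduce the plan's intervals.** The Wilson score interval is

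(x + z²/2)/(n + z²) ± [z/(n + z²)] × √(x(n − x)/n + z²/4), with z = 1.96.

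- 19/24: centre 20.92/27.84 = 0.751, half-width 0.156, giving 59.5% to 90.8%, as stated.
- 12/24 gives 31.4% to 68.6%, the stated widest interval.
- 38/48 gives 65.7% to 88.3%, the stated Cohort 1 survey interval.

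Exact (Clopper-Pearson, 57.8% to 92.9%) and Wald (62.9% to 95.4%) intervals for 19/24 do not match. The Cohort 3 interval is therefore returned over approached: the 19 recruited are the numerator and the 24 the denominator.

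**2. Apply each section's wording to the same data (19 returns from 24, only Cohort 3 surveyed).**

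| Wording followed | Calculation | Rate |
|---|---|---|
| Table 7 with the 14.1.1 meaning of recruited | 19/19 | 100% |
| Table 7 with the 6.1.3 and 12.1.3 meaning of participants | 19/24 | 79.2% (59.5% to 90.8%) |
| 5.3, pooled over WP1 | 19/(72 + 19) = 19/91 | 20.9% (13.8% to 30.3%) |
| 5.3, pooled, all 24 counted as recruited | 19/(72 + 24) = 19/96 | 19.8% (13.1% to 28.9%) |

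**3. Vary the number returned, k.**

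| k | k/k | k/24 | k/(72 + k) |
|---|---|---|---|
| 1 | 100% | 4.2% | 1.4% |
| 10 | 100% | 41.7% | 12.2% |
| 19 | 100% | 79.2% | 20.9% |
| 24 | 100% | 100% | 25.0% |

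Only the k/24 column measures survey return.

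**4. Survey Cohort 1 as well, with 38 returns.** Total returns are 38 + 19 = 57.

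- Table 7 with 14.1.1: 57/(48 + 19) = 57/67 = 85.1%.
- Table 7 with the 24 as participants: 57/(48 + 24) = 57/72 = 79.2%.
- 5.3 over WP1: 57/91 = 62.6%.

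The answer to who is surveyed therefore changes the result as much as the denominator does.

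**5. Count needed.** 0.80 × 24 = 19.2, so 20 returns (20/24 = 83.3%) meet 80%, while 19 (79.2%) do not.

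**The case against.** Table 7 carries its own qualifier, being given the survey, which would be idle if everyone counted had already returned one. Sections 6.1.3 and 12.1.3 call patients participants when the survey is handed over, and Table 2 lists receipt and return as separate events. On that reading Table 7 is 19/24 and can fail. This stands: 100% is one reading, reached only by carrying the parenthesis in 14.1.1 into Table 7. But the parenthesis is the Protocol's only definition of recruitment to Cohort 3, and the implied-consent rule in 9.1.1 supports it.

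The 20.9% is also one reading. Taken within Cohort 3 alone under the 14.1.1 definition, section 5.3 gives 100%.

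The gap between 19 and 20 is rounding; 38/48 is also 79.2%. Table 7 lists indicators that are not formally tied to funding. Both points stand, so the threshold matter is minor.

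Three stronger inferences are tempting, and the document does not support them:

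- *That the criterion can never be passed under 5.3.* Section 5.3 is a descriptive outcome without a threshold; the 80% belongs to Table 7.
- *That acceptability would be reported as experience of the device by people who never had the test.* Section 12.1.3 describes the survey as seeking views on the study and the intended use of the equipment, section 8.1.1 labels the cohort openly, and the section 5.3 acceptability indicators come from the discussion groups.
- *That section 15.4 wrongly draws economic data from "WP1 patient surveys, to identify key cost drivers".* Section 9.1.1 excludes identifiable and clinical data, not every cost item, and the survey itself is not shown.

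**Conclusion.** The point holds as an inconsistency in denominator and population. One planned result, 19 returns from 24, reads as 100%, 79.2% or 20.9% according to the section followed. The 100% assumes the 14.1.1 definition within Table 7. The 20.9% assumes section 5.3 is pooled over all of WP1 with only Cohort 3 surveyed. The 79.2% takes the patients handed a survey as the base and is the only one of the three that measures survey return.

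Independently of the denominator, current sections conflict on whether the device cohorts are surveyed, and the Cohort 1 interval of 65.7% to 88.3% has no matching procedure. The document does not show that the criterion must succeed or must fail; it shows that the result is undefined until the wording is settled. This should be corrected before the progression criteria are read. It does not affect the primary outcome.

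**What to change.** 1. In sections 5.3 and 14.1.1 and in Table 7, define the rate as surveys returned divided by surveys handed out to eligible patients. The electronic Cohort 3 log in section 9.2.1 can supply both counts.
2. In section 14.1.1, stop defining Cohort 3 recruitment as survey return. The interval for 19/24 can stay, labelled as returned over handed out.
3. State that 20 of 24 returns meet 80%, or say that 19 is accepted as 80% after rounding.
4. Reconcile sections 3.2 and 6.2 and the Cohort 1 sample-size text with the procedures. Either delete the Cohort 1 survey sentence and interval and restrict 3.2 and 6.2 to Cohort 3, or hand the survey to the device cohorts too, amend 12.1.3, 12.5 and Tables 2 and 8 to match, and report those cohorts separately from Cohort 3, whose respondents have not had the OLO test.

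The cost is Protocol wording. Surveying the device cohorts would add about 30 minutes per participant, the completion time given in section 12.1.3.

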#### **14.1.2 WP2 and WP3 discussion group meetings**

Approach 20 patients/carers (WP2) or healthcare workers (WP3). Recruit 10-15 participants max to each group. Detailed statistical analysis will not be conducted for WP2 and WP3 due to the qualitative nature of the research. Further details of qualitative analysis of discussion group recruitment and attendance data is provided in Section 15.1.

## **14.2 Missing, unused & spurious data**

The OLO ( System Operating Manual describes the expected white blood cell values for normal adults

The values may vary due to a wide range of factors, such as sex, diurnal variations, exercise, physical stress or trauma, pregnancy, indigestion of food, and cigarette smoking. The OLO-U1 Analyzer automatically assesses the OLO result against one of two pre-defined ranges (female age 22 years+ or male age 22 years+) and flags values outside of these normal values.

When capillary skin puncture is performed, several defence systems in the body are activated very quickly. These defence systems cause an increase in the number of WBCs in the blood closest to the wound, leading to greater differences in results from several samples taken from the same finger stick.

The participating sites normal laboratory ranges for a white blood cell and differential blood count will be sent to the CTR during site set up and will be taken into account when analysing the trial data.

For the purpose of ADVANCE the OLO-U1 Analyser will be programmed to compare the results against these standard local lab ranges for adult males and females.

A detailed Statistical Analysis Plan (SAP) [36] will be in place prior to the main trial database lock and analysis.

### **14.3 Procedures for reporting deviation(s) from the original SAP**

These will be submitted as substantial amendments where applicable and recorded in subsequent versions of the protocol and SAP.

### **14.4 Termination of the trial**

There will be no formal stopping rules or discontinuation criteria based on the low risk non-CTIMP trial design, however the TMG will assess SAE data at TMG meetings during the recruitment and follow up phase and escalate if deemed appropriate.

### **14.5 Inclusion in analysis**

Data derived from all participants in WP1-3 will be included in the analysis unless consent to do so has been specifically withdrawn on the ADVANCE Withdrawal CRF [28].

## **15 Analysis**

### **15.1 Quantitative analysis of WP1 device cohort evaluation**

All quantitative analysis will be documented in the SAP [36] prior to implementation of the analysis.

As this is a feasibility study, statistical analysis of study outcomes will be descriptive in nature. Continuous data will be reported as means and standard deviations, or medians and interquartile ranges, as appropriate. Categorical data will be reported as frequencies and proportions. Outcomes will be estimated with their associated 95% confidence intervals.

No formal hypothesis testing will take place.

While subsequent funding is not formally linked to satisfying any specific progression criteria, we propose the following as indicators that a larger study is feasible (NB. Failure to meet one or more of the criteria would indicate that modifications are required, with potentially further feasibility testing, prior to a larger study) as described in Table 7.

**Table 7.** Trial progression criteria

Outcome	Criteria
Recruitment	At least 80% of patients approached to take part provide consent
Intervention adherence	At least 90% of recruited participants receive the OLO test
Intervention fidelity	A valid test result is obtained from at least 90% of recruited participants who receive the OLO test
Survey fidelity	A survey is completed and returned from at least 80% of recruited participants who are given the survey
Data collection	At least 80% of recruited participants have clinical outcome data available for statistical analysis
Staff focus groups	Focus group data indicates that the OLO test is acceptable
Patient focus groups	Focus group data indicates that the OLO test is acceptable

There will be no interim analyses other than TMG review of WP1 SAE's at TMG meetings, Trial Manager review of screening logs through the WP1-3 recruitment phases, and Trial Manager review of data entry after approximately half of the participants have been recruited to WP1.

### **15.2 Qualitative analysis of WP1 Patient Acceptability Survey**

All qualitative analysis will be documented in the Qualitative Analysis Plan (QAP) [37] prior to implementation of the analysis.

### **15.3 Qualitative analysis of WP2 and WP3 discussion group meeting data**

The qualitative component of this trial aims to assess the acceptability of the System for the purpose of management of chemotherapy-related neutropenic sepsis to patients, carers and healthcare workers. Anonymised handwritten notes, taken at the meeting by the meeting leaders and/or observers, will be transcribed by meeting leader into electronic digital format (for example Microsoft Word). Data will be summarised to identify problems with the OLO (System and trial procedures that need addressing as well as patient, carers and healthcare workers attitudes and experiences. A more detailed framework analysis will not be conducted due to the feasibility nature of the study and limited funds. Anonymised data will be represented by selected extracts. The results will be discussed with data extracts used in support of claims made. The TMG will analyse the results to assess potential alterations to the trial design to inform the development of a larger UK-wide funding application, to include an amended survey and full framework analysis, and to complement the reporting of the full trial.

Potential publications resulting from the qualitative study will not be reported before the completion of the main trial if any aspect of this will cause a negative affect or compromise the trial in any way. The decision to publish results arising from the qualitative elements of the study before the end of the main trial, or not, will be made by the TMG and Executive Group.

#### **15.4 Cost effectiveness analysis**

In WP4 the TMG will analyse health utility and economic data (for example bed usage, antibiotic treatment and blood test costs) collected in WP1 via various routine UKONS data collection, a local audit of UKONS data run in parallel to the WP1 device cohort study, and WP1 patient surveys, to identify key cost drivers. The results will be used to inform the design of a future larger UK-wide trial, including anticipated effect sizes for the larger trial, which will include a cost utility study.

## **16 Data Management**

### **16.1 Data collection**

Data collection procedures will be documented in the Data Management Plan (DMP) [38].

Source Data is defined as *“All information in original records and certified copies of original records of clinical findings, observations or other activities in a clinical trial necessary for the reconstruction and evaluation of the trial. Source data are contained in source documents.”* There is only one set of source data at any time for any data element.

The ADVANCE trial will collect several different types of source data from a variety of sources as defined in Tables 8 and 9 below:

**Table 8.** ADVANCE WP 1 Source Data

	Medical records/ local UKONS data	Miscellaneous NHS database	Laboratory database	Pharmacy records (e.g. CANISC Chemocare)	MASCC Risk Assessment	OLO System (device)	ADVANCE database	ADVANCE WP1 paper/CF	ADVANCE Paper WP1 Withdrawal CRF	SAE Electronic CRF	ADVANCE WP1 screening log	Participant Surveys
Cohort 1												
Pre- hospital admission triage	X	X										
Hospital admission	X	X										
Standard laboratory tests including FBC, U+Es, LFTS, CRP, microbiology culture	X	X	X									
Antibiotic prescribing	X	X		X								
Care escalation (e.g. critical care)	X	X										
Senior clinical review including MASCC risk assessment	X	X			X							
Cohort 2												
Borderline neutropenic sepsis data	X	X										
Chemotherapy repeat assessment data	X	X										
Cohorts 1 and 2												
Trial screening / eligibility	X	X									X	
Trial consent							X				X	
Trial registration							X				X	
Baseline date (prior sepsis, toxicities)	X	X	X	X								
OLO System study blood sample and tests						X	X					
Hospital discharge	X	X										
Standard local follow-up	X	X										
Trial follow-up							X					
Trial adverse events										X		
Trial withdrawal								X				
Cohort 3												
Participant acceptability												X

**Table 9.** ADVANCE WP2 and 3 Source Data

	NHS database	VPLG database/records	ADVANCE database	ADVANCE paper ICF and/or reply slip	ADVANCE WP2 Paper Withdrawal CRF	ADVANCE WP3 Paper Withdrawal CRF	ADVANCE & WP2 screening log	ADVANCE & WP3 screening log	Leader/observer notes recording	Digital summary or notes
WP2 Patient/Carer Focus Group										
Trial screening/eligibility		X					X			
Trial consent				X						
Patient/carer acceptability									X	X
Trial withdrawal					X					
WP3 Focus Groups										
Screening/eligibility	X							X		
WP2/WP3 consent				X						
Healthcare worker acceptability									X	X
Trial withdrawal						X				

